## 7.6.4 All-cause Mortality

The percentage of 30- and 60-day all-cause mortality will be calculated based on each subject's date of death relative to C1D1 (ie, date of death minus date of C1D1).

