9.4.15. Long-Term Follow-up of Health Status

For subjects who remain on study, beginning 3 months after the discontinuation of study treatment, the subject's health status will be collected by telephone every 3 months until death, or the subject withdraws consent, or until the end of the study, whichever occurs first. The following health information will be collected and recorded in the source documents and eCRF:

- Survival information.
- Date of disease progression if subject did not have disease progression at the time they discontinued study treatment.

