11.3. Schedule of Analyses

This is an open-label study. Ongoing analyses to help manage the study and support the DSRC reviews for safety and antitumor activity will be undertaken. A final analysis will be conducted after all subjects have completed the study.

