## 1.0 INTRODUCTION

The purpose of this document is to provide details of the planned analyses for the Phase 1 and 2 ASTX029-01 study. The study is to assess the safety, PK, pharmacodynamics, and preliminary clinical activity of ASTX029 administered orally to subjects ≥18 years of age with advanced solid malignancies who are not candidates for approved or available therapies.

The primary objectives of the Phase 1 portion of this study are to assess safety and to identify the MTD, the RP2D, and the recommended dosing regimen of ASTX029 administered orally. The primary objective of the Phase 2 portion of this study is to assess preliminary clinical activity, as determined by objective response rate (ORR) in tumors characterized by gene aberrations in the MAPK signal pathway that may confer sensitivity to ASTX029.

The analyses specified in this document supersede the high-level analysis plan described in the protocol. Analyses and statistical reporting for ASTX029-01 subjects, with the exception of the analyses that are described in a separate Pharmacometrics Analysis Plan (PAP), will be conducted by Taiho Oncology Biostatistics department using SAS version 9.4 or higher.

This Statistical Analysis Plan (SAP) is based on the ASTX029-01 protocol amendment 5.0 (dated 14 April 2022).

Specifications for data tables, listings and figures are detailed in a separate document.

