#### 6.0 SCHEDULE OF ANALYSES

Analysis will be conducted after all subjects have completed at least one RECIST assessment. The expected study duration is approximately 3.5 years (42 months), including approximately 36 months for recruitment and approximately 6 months for safety follow-up. The study started in Q2 2018.

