#### 7.5.3 Survival

The OS is defined as the number of days from the day study drug was first taken to the date of death (regardless of cause). Subjects without a documented death date will be censored on the last date they were known to be alive. The OS will be presented using a Kaplan Meier estimate. The 95% CI for median OS will be provided using the Kaplan-Meier method with the log-log transformation. All subjects in the Efficacy Analysis Set (Section 5.3) will be included in the OS analysis. The OS rate at 3, 6, 9 and 12 months (and in subsequent 6-month increments if there are participants still at risk) will be estimated with corresponding two-sided 95% CIs.

Frequency (number and percentage) of participants with death events and censoring reasons will be presented with the overall event and censor rates. The event and censoring reasons are as follows:

- Death
- Ongoing and no death
- Withdrawal of consent
- Lost to follow-up.

The OS time or censoring time and the reasons for censoring will also be presented in a listing

The PFS is defined as the number of days from the start of the study drug to disease progression or death, whichever occurs first. The PFS will be analyzed using a Kaplan-Meier method, with PFS time being censored on the date of the last disease assessment. The 95% CI for median PFS will be provided using the Kaplan-Meier method with the log-log transformation. All subjects in the Efficacy Analysis Set (Section 5.3) will be included in the PFS analysis.

Progression of disease (PD) is included as an overall response in Table 1 above, and combines evaluation target, non-target, and new lesions. Target lesion response of PD is at least a 20% increase in the sum of diameters of target lesions, taking as reference the smallest sum on study (this includes the baseline sum if that is the smallest on study). Non-target lesion response of PD is unequivocal progression of existing nontarget lesions. The appearance of 1 or more new lesions is also considered progression of disease. Additional details can be found in Appendix 3 of the protocol, which is based on RECIST v1.1 (Eisenhauer et al 2009).

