## 7.6 Safety Variables and Analyses

Safety Analysis will be performed using the Safety Analysis Set (Section Error! Reference source not found.). Safety is assessed by subject-reported and investigator-observed AEs, along with physical examinations, clinical laboratory tests (hematology, coagulation, chemistries, and urinalysis), vital signs, concomitant medications, ECOG performance status, and ECGs. Exposure to study drug, TEAEs, deaths, and causes of deaths will be tabulated.

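### Counting lost or withdrawn subjects as survivors can only lower the SAP's 30- and 60-day mortality; adding days 30 and 60 to the Kaplan-Meier OS output would avoid this

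*SAP*

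**What the plan says.** SAP 7.6.4 gives the whole definition in one sentence: "The percentage of 30- and 60-day all-cause mortality will be calculated based on each subject's date of death relative to C1D1". It names no denominator, minimum follow-up, censoring rule or handling of unknown vital status.

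The denominator has to be inferred. SAP 7.6 states "Safety Analysis will be performed using the Safety Analysis Set", and SAP 5.4 defines that set as everyone who received any study drug. SAP 7.7 plans no imputation that would apply here and keeps subjects lost to follow-up in the analyses up to the data cut-off. Protocol 11.11 stops at the day of last contact instead, but SAP 1.0 says "The analyses specified in this document supersede the high-level analysis plan described in the protocol".

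SAP 7.5.3 treats the same subjects differently for overall survival, which also runs from first dose: "Subjects without a documented death date will be censored on the last date they were known to be alive". Its planned survival rates start at 3 months, so no censored estimate at 30 or 60 days is specified.

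On timing, SAP 6.0 says "Analysis will be conducted after all subjects have completed at least one RECIST assessment".

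**The concern.** A simple percentage estimates 60-day mortality without bias only if every subject's status at day 60 is known. Here a subject who withdraws consent on day 20 and dies unrecorded on day 40 stays in the denominator and adds nothing to the numerator. No compensating error runs the other way, so the reported figure can fall below the true one but cannot exceed it on this account.

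This is a safety summary in a first-in-human trial, tabulated by cohort, and some Phase 2 cohorts may hold only 10 subjects. The mortality table may also disagree with the OS curve at day 60, although both use the same subjects and time origin, and nothing in the SAP prepares the reader for that.

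**Working it through.** The plan states no mortality, dropout or follow-up figure on this point, so there is nothing to reproduce. The rates below are assumptions, shown over a range.

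**Loss before day 60.** Let m be the true 60-day mortality and d the proportion lost by day 60 in the absence of death, both with constant hazards:

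- h = −ln(1 − m)/60 and c = −ln(1 − d)/60.
- Expected crude percentage at day 60 = [h/(h + c)] × [1 − (1 − m)(1 − d)].

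For m = 10% and d = 10%, h = c, so the result is 0.5 × (1 − 0.90 × 0.90) = 0.5 × 0.19 = 9.5%. The same formula gives:

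| True 60-day mortality | 5% lost | 10% lost | 20% lost |
|---|---|---|---|
| 5% | 4.88% | 4.75% | 4.49% |
| 10% | 9.75% | 9.50% | 8.98% |
| 20% | 19.51% | 19.02% | 18.00% |

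The 30-day figure moves the same way, but less. With m = d = 10% at day 60, true 30-day mortality is 1 − √0.90 = 5.13%, and the crude percentage is 0.5 × (1 − √0.81) = 5.00%.

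**Small cohorts.** For a given loss proportion the expected bias does not depend on cohort size, but one subject weighs more. An unrecorded death is worth 1/10 = 10 points in a first-stage cohort and 1/29 = 3.4 points in a full one.

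**The SAP 6.0 trigger.** The first post-baseline scan is due at the end of Cycle 2: 2 × 21 = day 42, ±7, so day 35 to 49. At the earliest permitted analysis the last subject is 60 − 49 = 11 to 60 − 35 = 25 days short of day 60. Day 30 is always passed, so 30-day mortality is unaffected.

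With uniform accrual, the number with under 60 days is N × (60 − F)/(months × 30.4375), where F is the day of the last subject's scan. Taking F = 35, the worst case:

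- 300 subjects over 55 months (Protocol 12): 300 × 25/1,674 = 4.5, or 1.5%.
- 300 subjects over 36 months (SAP 6.0): 300 × 25/1,096 = 6.8, or 2.3%.
- One cohort of 29 over an assumed 6 months: 29 × 25/183 = 4.0, or 13.7%.

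At a true 60-day mortality of 20%, mortality by day 35 is 1 − 0.80^(35/60) = 12.2%. Affected subjects' follow-up is spread between days 35 and 60, so the average unseen risk is about (20 − 12.2)/2 = 3.9 points. The study-wide shortfall is 1.5% × 3.9 = 0.06 or 2.3% × 3.9 = 0.09 point. In the fast single cohort it is 13.7% × 3.9 = about 0.5 point.

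**Planned dates.** SAP 6.0 puts the start in Q2 2018. Adding 55 months of recruitment ends enrolment between about November 2022 and January 2023. The SAP version history dates approval at 2 April 2024, some 14 months or more later. On those dates every subject had passed day 60 before the SAP was approved.

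**The case against.** A reader might infer that the trigger in SAP 6.0 leaves the last subjects with only 35 to 49 days of follow-up and so builds in an understatement of early mortality. The documents do not support that. The trigger is the earliest permitted time, not a cut-off date. The same section expects "approximately 36 months for recruitment and approximately 6 months for safety follow-up", and Protocol 11.3 says "A final analysis will be conducted after all subjects have completed the study". On the planned dates the shortfall does not arise. It would need recruitment to have overrun by more than a year, which neither document states.

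A reader might also infer that deaths after early discontinuation are missed, because Protocol 9.4.15 provides that "beginning 3 months after the discontinuation of study treatment, the subject's health status will be collected by telephone every 3 months". That leaves a gap after the 30-day visit, but it delays knowledge of a death rather than erasing it: a death on day 50 is recorded with its date at the later call. Protocol 5.4.1 keeps subjects in follow-up after stopping treatment, and Protocol 5.4.2 asks for survival information even after withdrawal. Only genuine withdrawal or loss before the time point matters, and its rate is unknown.

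It can fairly be added that the Kaplan-Meier OS curve, the OS listing and the deaths listing are already planned, so a reader could find day-60 survival there. The separate table specifications mentioned in SAP 1.0 may also state a denominator. These points limit the consequence. They do not change SAP 7.6.4, which remains an uncensored percentage with no early landmark beside it.

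Kaplan-Meier is not neutral either. If deaths are reported promptly while survivors are censored at an older last contact, it can overstate mortality. That objection stands and shapes the recommendation.

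**Conclusion.** The concern holds as a minor one. As written, SAP 7.6.4 counts subjects withdrawn or lost before day 30 or 60 as survivors, and any resulting error is downward. At an assumed true 60-day mortality of 10%, the understatement is about 0.25, 0.5 and 1.0 point for 5%, 10% and 20% loss. It scales roughly with both rates and vanishes if nobody is lost. These sizes rest on assumed mortality and loss, constant hazards, loss unrelated to prognosis, and the inferred all-treated denominator. The documents do not show that understatement will occur, only that the rule permits it and cannot correct it. The trigger should not carry the argument, and no design or power claim is affected.

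**What to change.** In SAP 7.6.4, report 30- and 60-day all-cause mortality as 1 minus the Kaplan-Meier OS estimate at days 30 and 60 from first dose. Use the SAP 7.5.3 censoring at last date known alive and its log-log 95% confidence interval, and give the number at risk at each day. Keep the crude death counts beside it, with the denominator stated.

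Showing both matters. Kaplan-Meier assumes non-informative loss and can err upward when deaths are learned of sooner than survivors are contacted; the crude percentage errs downward. In a cohort with no deaths by the time point the log-log interval is undefined, and the crude count then serves.

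The cost is a sentence or two in the SAP and two more time points in the OS output already planned. The reported mortality may come out slightly higher.

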## 7.6.5 Concomitant Medications

Concomitant medications are medications taken with a start date on or after the date of the first dose of study drug or those with a start date before the start of the administration of study drug and a stop date on or after the start of the administration of study drug. Medications taken beyond 30 days from the last dose of study drug or after the start of a post-treatment alternative anti-cancer treatment are not considered concomitant medications, unless they are used for treating a related SAE. For the purpose of inclusion in the concomitant medication tables, incomplete medication start and stop dates will be imputed conservatively following the data programming conventions as detailed in the Taiho Data Programming Standards.

Concomitant medication will be coded by the latest version of the World Health Organization (WHO) Drug Dictionary before the data download and summarized by Anatomical Therapeutic Chemical (ATC) level 2 and drug name, sorted alphabetically, using counts and percentages.

## 7.6.6 Laboratory Tests

Shift tables will display (1) shift from baseline grade to the worst grade during the study, and (2) shift from baseline grade to the last grade at the end of study.

Laboratory values recorded as an interval such as "\ge x", "\le x", or "2+" will be handled, if necessary for calculation purposes, following the data programming standards as detailed in the ADaM data reviewer guide.

#### 7.6.7 Vital Signs

Vital signs will be summarized by visit and treatment group using proportion of subjects with each vital sign being too high or too low according to conventionally accepted vital sign normal ranges as follows:

- Pulse rate 110 bpm or greater.
- Pulse rate 50 bpm or less.
- Diastolic blood pressure 110 mmHg or greater.
- Diastolic blood pressure 55 mmHg or less.
- Systolic blood pressure 180 mmHg or greater.
- Systolic blood pressure 80 mmHg or less.
- Respiration rate 20 breaths/min or greater.
- Body temperature 39°C or greater.

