In conclusion, the main findings in toxicity evaluation studies in both species tested were consistent with the expected pharmacological action of ASTX029 (ie, findings in bone, soft tissue mineralization, skin lesions, and ulceration of the GI tract). Other findings, such as minimal effects on liver function with no associated histopathology correlates, may be due to the chemical toxicity of ASTX029. For an ERK inhibitor, tissue mineralization is a known class effect relating to perturbation of phosphate handling linked to vitamin D levels and FGF-23 inhibition (Diaz et al 2012; Yanochko et al 2013). In addition, delayed skin lesions (rash) have also been seen clinically with ERK and MEK inhibitors (Sullivan et al 2018; Li et al presentation 2017; Varga et al 2020; MacDonald et al 2015; Manousaridis et al 2013). Since the lower (in terms of human equivalent dose) NOAEL (and the HNSTD) was seen in the dog, this species is considered more sensitive than the rat to the toxicity of ASTX029 based on dose alone. However, considering the overlapping observed systemic exposures in rat and dog pivotal studies at the HNSTD in dogs and the NOAEL in rats and also the apparent gender differences seen in both species, the distinction of the dog as the more sensitive species is tentative. In addition, some key findings in the rats (tissue mineralization, skin lesions), which are consistent with known class effects of MAPK pathway inhibitors, can be considered relevant to the clinic.

Therefore, due to the overlapping exposures at toxicologically meaningful doses in rats and dogs, both species have been considered for calculation of the proposed starting dose for the FIH clinical trial.

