9.4.9. Schedules of Events

Table 11 presents the complete schedule of events for Regimen 1 Continuous Dosing, andTable 12 presents that for Regimen 2 Intermittent Dosing with details following in text. Table 13presents the Schedule of Events for the Study Extension phase.

Clinical and diagnostic laboratory evaluations are detailed before study entry, throughout the study, and at the follow-up evaluation. The purpose of obtaining these detailed measurements is to ensure adequate assessments of preliminary clinical activity, safety, and tolerability. Repeat clinical evaluations and laboratory studies more frequently if clinically indicated.

Note any deviation from protocol procedures. Investigators are responsible for implementing appropriate measures to prevent the recurrence of violations and deviations and to report to their IRB/IEC according to policy.

Table 11: Schedule of Events Regimen 1 – Continuous (Days 1 Through 21) Dosing

Cycle (21 Days) ^a]	1			2	2		≥3 ª	Tx Term ^b	30-day Safety FU ^c	Long- term FU
Cycle Day ^d		1 ^e	2	8	15	1	2	8	15	1			
Study treatment dispensation		x		x	Х	x		x	x	X			
Dosing compliance information				x	х	x		x	x	X	х		
Procedures	Screening ^f												
Informed consent	Х												
Medical history	Х												
Investigator's confirmation of eligibility	Х	x											
PE/symptom-directed PE ^g	Х	x		x	х	x		x	x	x	x	х	
Height	Х												
Weight	Х	x				x				x			
Vital signs ^h	Х	x	x	x	х	x	x	x	x	x	x	х	
ECOG performance status	Х	x		x	х	x		x	x	x	x	х	
12-lead ECG ⁱ	Х	x	x	x	х	x				x	x		
ECHO or MUGA scan	Х	Repe	Repeat every 2 cycles for the first 4 cycles and then every 4 cycles thereafter $(\pm 7 \text{ days})$					x					
Ophthalmic examination ^j	Х												
Concomitant medications/AEsk	Х	x	x	x	х	x	x	x	x	x	x	х	
Randomization (if applicable), enrollment	Х												
Laboratory Assessments													
Hematology ^{1,m}	Х	x		x	X	x		x	x	x	X		
Coagulation ^{m,n}	Х	x				x				х	х		

Cycle (21 Days) ^a			-	1				2		≥3 ª	Tx Term ^b	30-day Safety FU ^c	Long- term FU
Cycle Day ^d		1 ^e	2	8	15	1	2	8	15	1			
Chemistry ^{m,o}	Х	x		x	x	x		х	х	х	х		
Urinalysis ^{m,p}	х	x				x				X	Х		
Serum or urine pregnancy test ^{m,q}	х	x				x				X	X		
Pharmacokinetics ^r		x	x			x	xs			x ^t			
Blood sample for ctDNA ^u	х	x				x				х	X		
Blood (PBMC) sample for germline DNA	х												
Obtain archival tumor tissue ^v	х												
Collect pretreatment biopsyv	х												
Collect on-treatment biopsyv								x					
Disease Assessments													

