^e On C1D1 (the first day of study treatment administration), complete the PE, vital signs, weight, and laboratory evaluations before administration of study treatment. Laboratory evaluations do not need to be repeated if screening tests are within 4 days prior to first dose of ASTX029. For subjects who had a full PE performed at screening within 4 days prior to the first dose of ASTX029, it is not necessary to repeat the full PE on C1D1; a symptom-directed PE on C1D1 can be done instead.

- ^f Screening procedures must occur within 21 days prior to first dose of ASTX029.
- ^g At screening, a complete PE per the institutional standard practice, but including a skin examination (Section 9.4.1), will be performed. After screening, symptom-directed PEs will be performed at the time points indicated and at the investigator's discretion.
- ^h Obtain vital signs at screening; predose on Day 1 of each cycle and on C1D2, C1D8, C1D15, C2D2, C2D8, and C2D15; at the Tx Term visit; and at the Safety Follow-up visit. In addition, obtain systolic/diastolic blood pressure and heart rate at 1 hour (±30 minutes) postdose on C1D1 and C2D1. Assess all vital signs after the subject has rested in a sitting or semirecumbent position for at least 3 minutes.
- ¹ The 12-lead ECGs will be performed at screening and predose and 2 hours (±30 minutes) postdose on C1D1 and C2D1; they will be performed predose at all other time points on the dosing days and at the Tx Term visit as indicated. All ECGs will be recorded at 25 mm/second in triplicate, with each recording separated by at least 30 seconds, while the subject is in a semirecumbent position (Section 9.4.4). Two copies of the ECG tracing should be obtained at the time of the ECG; the first copy will be kept in the subject's medical chart and the second copy will be kept in the study file for retrospective collection by the sponsor if necessary. On C1D1, ECG findings must meet study entry criteria before dosing.
- ^j An ophthalmic examination will be performed at screening. Additional ophthalmic examinations will be performed only as symptomatically warranted. Refer to Section 9.4.6 for details.

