11.7. Safety Analyses

Safety will be assessed by subject-reported and investigator-observed Aes along with concomitant medications, Pes, clinical laboratory tests (hematology, coagulation, serum

chemistry, and urinalysis), vital signs, ECOG performance status, ECGs, and ECHO/MUGA scans.

All Aes will be mapped to the appropriate System Organ Class (SOC) and Preferred Term (PT) according to the Medical Dictionary for Regulatory Activities (MedDRA). Severity of Aes will be graded using CTCAE v4.03 (Appendix 2). All Aes collected during the study will be presented in data listings. TEAEs are defined as events that first occur or worsen after the subject receives study drug on C1D1 until 30 days after the last dose of study treatment, or the start of an alternative anticancer treatment, whichever occurs first, to be defined in more detail in the statistical analysis plan. Summaries will be provided by SOC and PT for all Aes, Aes considered related to study treatment, SAEs, and related SAEs as follows based on the treatment period when the events occur. Similar summaries will also be generated by maximum severity. In addition, exposure to ASTX029, reasons for discontinuation, deaths, and causes of deaths will be tabulated.

The number and proportion of subjects who have DLTs, as defined in Section 7.4, will be summarized by cohort and regimen in Phase 1 Part A.

Laboratory values reported by different local labs will be listed. Shift tables will be provided for each graded laboratory test.

Concomitant medications are the medications taken with a start date on or after the start of the administration of study treatment (C1D1) or those with a start date before the start of the administration of study treatment (C1D1) and a stop date on or after the start of study drug administration (C1D1) as to be defined in more detail in the statistical analysis plan. Concomitant medication will be coded by the World Health Organization (WHO) Global List and summarized by therapeutic subgroup (Anatomical Therapeutic Chemical [ATC] level 2) and PT, sorted alphabetically, using counts and percentages.

Vital sign measurements will be summarized by visit using the proportion of subjects with each vital sign being too high or too low according to conventionally accepted vital sign normal ranges. Physical examination, ECOG performance status, and ECG findings will be listed in data listings or analyzed with summary tables.

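### Vital signs are summarised only as proportions beyond wide cut-offs by visit, so a moderate shift in the paired predose and 1-hour postdose blood pressure or heart rate is unlikely to be visible by cohort

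*SAP*

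**What the plan says.** SAP 7.6.7 states: "Vital signs will be summarized by visit and treatment group using proportion of subjects with each vital sign being too high or too low". It then lists fixed limits, for example "Systolic blood pressure 180 mmHg or greater" and "Respiration rate 20 breaths/min or greater". The low systolic limit is 80 mmHg, the diastolic limits are 110 and 55 mmHg, and the pulse limits are 110 and 50 bpm. Protocol 11.7 has the same form: "Vital sign measurements will be summarized by visit using the proportion of subjects with each vital sign being too high or too low". The SAP therefore adds the numeric limits; it does not cut back a fuller plan.

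For Regimen 1, the only regimen opened (SAP 7.9), vital signs are taken before dosing on Day 1 of each cycle. Protocol Table 11, footnote h, adds a second reading: "In addition, obtain systolic/diastolic blood pressure and heart rate at 1 hour (±30 minutes) postdose on C1D1 and C2D1". The purpose given for the schedule in Protocol 9.4.9 is general: "The purpose of obtaining these detailed measurements is to ensure adequate assessments of preliminary clinical activity, safety, and tolerability".

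For laboratory values, SAP 7.6.6 says: "Shift tables will display (1) shift from baseline grade to the worst grade during the study", and adds a second shift to the last grade. No numeric change is planned. For ECG, SAP 7.6.8 already allows values and changes from baseline by visit, as an option. SAP 7.2 defines baseline as the last value up to and including the date of first dosing, with no reference to the time of the dose.

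**The concern.** Footnote h produces paired readings: the same subject, the same day, before and one hour after the dose. A by-visit proportion does not say which reading is counted, and it discards the pairing. The blood pressure limits are also far from where most subjects are likely to lie, so a shift affecting every subject can leave almost nobody beyond a limit.

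This is a first-in-human study with safety in its Phase 1 primary objective. Protocol 1.5 reports Grade 2 hypotension among the dose-limiting toxicities of another ERK inhibitor. On the laboratory side, Protocol 1.3.2.4 says that "tissue mineralization is a known class effect relating to perturbation of phosphate handling", and Protocol Table 10 collects both calcium and phosphorus. A grade-shift table cannot show movement within a grade.

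**Working it through.** **Plan's own figure.** The documents give one safety sizing calculation: 14 subjects in Part B for a 90% chance of seeing at least one adverse reaction of 15% incidence. It reproduces: 1 − 0.85^14 = 0.897. It is not in dispute; it supplies n=14. The full Phase 2 cohort supplies n=29.

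**Assumptions.** The documents give no vital-sign means or SDs. Assumed here: predose systolic mean 125 mmHg, between-subject SD 15 (unchanged postdose), true postdose fall 8 mmHg (range 5 to 10), SD of paired change 10 to 15, normal distributions.

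**Cut-off table, systolic at or below 80 mmHg.** Share = Φ((80 − mean)/15).
- Predose: Φ(−3.00) = 0.13%.
- After a fall of 8: Φ((80 − 117)/15) = Φ(−2.47) = 0.68%. Expected count 14 × 0.0068 = 0.10, or 29 × 0.0068 = 0.20.
- After a fall of 5 or 10: 0.38% or 0.98%.

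**Paired change.** Two-sided 5% paired t-test, noncentrality = (fall/SD of change) × √n.

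| n | SD of change | Noncentrality, fall 8 | Power, fall 8 | Power, fall 5 |
|---|---|---|---|---|
| 29 | 10 | 0.80 × 5.385 = 4.31 | 0.99 | 0.74 |
| 29 | 15 | 0.533 × 5.385 = 2.87 | 0.79 | 0.41 |
| 14 | 10 | 0.80 × 3.742 = 2.99 | 0.79 | 0.41 |
| 14 | 15 | 0.533 × 3.742 = 2.00 | 0.46 | 0.21 |

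The SAP plans no test here, so precision is the more natural scale. The 95% CI half-width is t × SD/√n. At n=29 it is 2.048 × 10/5.385 = 3.8 to 2.048 × 15/5.385 = 5.7 mmHg. At n=14 it is 2.160 × 10/3.742 = 5.8 to 2.160 × 15/3.742 = 8.7 mmHg.

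**Upper systolic limit.** Assume mean 125 (SD 15) to 130 (SD 18). After a 10 mmHg rise, the share at or above 180 is 0.14% to 1.3%. The chance that even one subject is counted, 1 − (1 − p)^n, is 2% to 17% at n=14 and 4% to 32% at n=29. Power of the paired change is 0.64 to 0.93 and 0.93 to 0.999. After a 30 mmHg rise, the chance of counting at least one is 50% to 87% at n=14 and 76% to 98% at n=29.

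**Less extreme limits.** With diastolic mean 75 and SD 10 (assumed), a fall of 8 moves the share at or below 55 from Φ(−2.0) = 2.3% to Φ(−1.2) = 11.5%, or from 0.7 to 3.3 subjects of 29. With pulse mean 78 to 85 and SD 12 to 14 (assumed), a rise of 10 bpm moves the share at or above 110 from 0.4%–3.7% to 3.3%–14.2%. These limits are more responsive, but a table that does not separate predose from postdose still would not show the contrast clearly.

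**The case against.** **Other routes capture part of this.** Clinically significant vital-sign findings are recorded as AEs (Protocol 9.3.1) and tabulated (SAP 7.6.2), so a Grade 2 hypotension would appear there. SAP 7.0 says the data behind tables are generally listed. ECG heart rate, with a 2-hour postdose reading on the same days, may be summarised as change from baseline. Table layouts are in a separate document (SAP 1.0), which might add a time-point split. This stands as mitigation. However, listings give no estimate, AEs take only clinically significant findings, and the ECG summary is optional and contains no blood pressure.

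**The prior evidence is weak.** The dog cardiovascular study of ASTX029 itself found no relevant effect on arterial pressure or heart rate (Protocol 1.3.2.3), and Protocol 8 lists no blood pressure effect. Serum calcium and phosphate changes occurred in the rat dose-range studies but not in the rat GLP study (Protocol 1.3.2.4). This lowers the urgency.

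**The Total column helps.** SAP 7.0 also summarises all subjects combined. Even with about 180 Phase 2 subjects, the assumed 8 mmHg fall gives 180 × 0.0068 = 1.2 subjects at or below 80 mmHg, against 180 × 0.00135 = 0.24 predose. The help is slight for systolic pressure and greater for diastolic pressure and pulse.

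**No control arm.** A 1-hour change cannot be separated from time-of-day, fasting or clinic effects. This stands, and it limits what the added tables can claim.

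A reader might also infer that the SAP weakened the protocol's plan, that the 1-hour reading was taken specifically to detect a drug effect, or that laboratory values have no change from baseline. The documents do not support these. Protocol 11.7 already plans the same summary, the stated purpose is general, and a grade shift is a categorical change from baseline; only numeric change is absent.

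**Conclusion.** The gap is real and descriptive. Vital signs have no planned numeric summary, and the paired readings on C1D1 and C2D1 have no stated paired analysis. On the assumed inputs, an 8 mmHg systolic fall leaves about 0.7% of subjects at or below the cut-off, or 0.1 of 14 and 0.2 of 29, while a paired change has power 0.46 to 0.79 and 0.79 to 0.99. The result is strongest for systolic pressure and weaker for diastolic pressure and pulse. Not every limit is extreme: the respiration limit is not.

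A reader might conclude that the plan cannot show any effect, or that the tables will be empty. That goes too far: a 30 mmHg systolic rise would often register, the diastolic and pulse limits respond to smaller shifts, and AEs and listings remain. Every mean, SD and shift used here is an assumption. The Phase 1 primary endpoint rests on DLTs and AEs, and the Phase 2 ORR analysis is not affected.

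**What to change.** - **SAP 7.6.7:** add descriptive tables of observed value and change from baseline for blood pressure and heart rate, by visit and time point, with predose and 1 hour shown separately. Add the within-day postdose-minus-predose change on C1D1 and C2D1 with a 95% CI. Keep the cut-off table.
- **Baseline for these tables:** define it as the last value before the first dose. Under SAP 7.2 the C1D1 1-hour reading falls on the first dosing date, so it could become the baseline and hide the change of interest.
- **SAP 7.6.6:** add numeric value and change from baseline for calcium and phosphorus beside the grade shifts.

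The cost is SAP wording and a few extra tables, with no new procedures or subjects. The text should say that, without a control arm, the change is descriptive and cannot by itself be attributed to the drug. In Part A cohorts of 3 or 6 subjects the intervals will be too wide to carry much weight.
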